10.3.1 Submission Schedule

The pathology samples should be submitted within one month of patient registration.

10.4 ECOG-ACRIN Sample Tracking System

It is **required** that all samples submitted on this trial be entered and tracked using the ECOG-ACRIN Sample Tracking System (STS). The software will allow the use of either 1) an ECOG-ACRIN user-name and password previously assigned (for those already using STS), or 2) a CTSU username and password.

When you are ready to log the collection and/or shipment of the samples required for this study, please access the Sample Tracking System software by clicking <https://webapps.ecog.org/Tst>

Important: Please note that the STS software creates pop-up windows, so you will need to enable pop-ups within your web browser while using the software. A user manual and interactive demo are available by clicking this link:

<http://www.ecog.org/general/stsinfo.html> Please take a moment to familiarize yourself with the software prior to using the system.

A shipping manifest form must be generated and shipped with all sample submissions.

Please direct your questions or comments pertaining to the STS to [contact].

10.4.1 Study Specific Notes

An Generic Specimen Submission Form (#2981) will be required only if STS is unavailable at time of sample submission. Indicate the appropriate Lab ID # on the submission form:

- 0001 = ECOG-ACRIN CBPF
- 0149 = Indiana University School of Medicine
- Retroactively enter all collection and shipping information when STS is available.

10.5 Banking

Blocks/slides submitted will be retained at the ECOG-ACRIN Central Biorepository for use in future ECOG-ACRIN approved studies. Blocks will be available for purposes of individual patient management on specific written request. If future use is denied or withdrawn by the patient, the samples will be removed from consideration for use in any future study.

11. Correlative Studies

NOTE: ECOG-ACRIN requires that all biological samples submitted be entered and tracked via the online ECOG-ACRIN Sample Tracking System. An STS shipping manifest form must be generated and shipped with the sample submissions. See Section [10.4](#).

11.1 The main goal of the study is to correlate the presence of genetic polymorphism, tamoxifen metabolites, and benefit from the drug.

Rev. 8/12

11.1.1 Sample Submission Schedule – Genotype Verification (Mandatory)

Whole blood must be collected at baseline, prior to treatment (strongly encouraged), but may be collected at the end of cycle three (3) if unable to collect at baseline.

All questions regarding sample collection, preparation and shipping should be sent to: [name], [contact], [contact], [contact], Email: [contact]

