CTSU Regulatory Office [name] [name] Phone – [name] Fax – [contact] Email: [contact] (for submitting regulatory documents only)	Please refer to the patient enrollment section of the protocol for instructions on using the Oncology Patient Enrollment Network (OPEN) which can be accessed at https://www.ctsu.org/OPEN_SYSTEM/ or https://OPEN.ctsu.org . Contact the CTSU Help Desk with any OPEN-related questions at [contact] .	ECOG-ACRIN Operations Office - Boston, FSTRF, [name] [name] (ATTN: DATA). [contact] [contact] Data should be sent via postal mail (preferred), however fax is accepted. Do not submit study data or forms to CTSU Data Operations. Do not copy the CTSU on data submissions.

The most current version of the study protocol and all supporting documents must be downloaded from the protocol-specific Web page of the CTSU Member Web site located at https://www.ctsu.org. Access to the CTSU members' website is managed through the Cancer Therapy and Evaluation Program - Identity and Access Management (CTEP-IAM) registration system and requires user log on with CTEP-IAM username and password.
		

For clinical questions (i.e. patient eligibility or treatment-related) contact the Study PI of the Coordinating Group.
		

For non-clinical questions (i.e. unrelated to patient eligibility, treatment, or clinical data submission) contact the CTSU Help Desk by phone or e-mail:
 
CTSU General Information Line – [name], or [contact]. All calls and correspondence will be triaged to the appropriate CTSU representative.
		

For detailed information on the regulatory and monitoring procedures for CTSU sites please review the CTSU Regulatory and Monitoring Procedures policy located on the CTSU members' website https://www.ctsu.org > education and resources tab > CTSU Operations Information > CTSU Regulatory and Monitoring Policy
		

The CTSU Web site is located at https://www.ctsu.org
		

Schema

1 cycle = 28 days

Accrual = 240

1. Open label tamoxifen 20 mg PO daily until progression, unacceptable toxicities or any other condition outlined in Section 5.5.
2. Collection of Baseline blood for the mandatory research studies should be done prior to protocol treatment (preferred), but may be done at the end of Cycle 3 visit. Additional blood is to be submitted at the end of Cycle 3 and at the end of treatment. See Section 7.2 and 11.

Rev. 8/12

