7.1 Therapeutic Parameters

1. Prestudy scans and x-rays used to assess all measurable or non-measurable sites of disease must be done within **4 weeks** prior to registration.
2. Prestudy CBC (with differential and platelet count) should be done \leq **4 weeks** prior to registration.
3. All required prestudy chemistries, as outlined in Section [3](#), should be done \leq **4 weeks** prior to registration.

NOTE: 1 cycle = 28 days

	Pre-Study		End of Cycles 1 and 2 ⁹	End of Cycle 3 ⁹	Every 3 cycles (after cycle 3) ⁹	At discontinuation of treatment ¹⁰	Post treatment up to 5 years from study entry
	\leq 4 weeks prior to registration	\leq 2 weeks prior to registration					
Height	X						
History, Physical Exam, ECOG PS, Vital signs, Weight	X		X	X	X	X	X ³
Concomitant Medications	X		X	X	X		X ⁸
CBC ¹	X			X	X	X	
Bilirubin, SGOT (AST), SGPT (ALT)	X			X	X	X	
Lipid profile ¹¹	X			X			
HCG ²		X					
Bone scan	X ⁶			X ⁶	X ⁶		X ^{6,8}
Tumor assessment by PE	X			X	X	X	X ⁸
Tumor assessment by CT or MRI ⁷	X			X	X	X	X ⁸
Research blood submissions ⁵	X ⁴			X		X	

- Rev. 8/12
1. CBCs (with differential and platelet count) which includes WBC, ANC, Platelets, Hgb, and Hct.
 2. All females of child-bearing potential must have a blood or urine test within 2 weeks prior to registration to rule out pregnancy.
 3. Every 3 months if patient is $<$ 2 years from study entry, every 6 months if patient is 2-5 years from study entry. No specific requirements if patient is more than 5 years from study entry.
- Rev. 5/11

- Rev. 8/12 4. It is strongly encouraged that the whole blood collected for the genotype verification is collected prior to protocol treatment, but may be collected at the end of cycle three (3) if unable to collect at baseline.
- Rev. 8/12 5. Refer to Sections [7.2](#) and [11](#) for submission instructions.
- Rev. 5/11, 6. Baseline bone scan required in all patients; repeat in follow-up as clinically indicated.
- 8/12 **NOTE:** If bone scan done within 6 months prior to registration showed no evidence suggesting bone metastases and no clinical indication of skeletal pain or other evidence suggesting bone metastases, a repeat baseline bone scan is not required.
- Rev. 5/11, 7. CT or MRI of chest/abdomen/pelvis are required at baseline. Those tests required to follow known site(s) of disease should be repeated at the end of Cycle 3 and then every 3 cycles during treatment and according to the follow up schedule if off treatment, until first progression of disease.

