- NOTE: If CT or MRI of chest and/or abdomen/pelvis done within 6 months prior to registration showed no evidence of disease in the area(s) and no clinical indication suggesting new metastases, full re-staging including all areas is not required; however, ensure that disease is evaluable per RECIST requirements (Section [6](#)).
- Rev. 5/11 8. Concomitant medication and tumor assessments are to be done up to (and including) the assessment which shows first progression of disease. If patient discontinues treatment due to reasons other than disease progression, concomitant medication and tumor assessments should be performed until disease progression on the following schedule: Every 3 months if patient is < 2 years from study entry, every 6 months if patient is 2-5 years from study entry. No specific requirements if patient is more than 5 years from study entry.
- Rev. 5/11 9. All tests should be performed at the end of the cycle. A +/- 7 day window will be allowed in case of scheduling problems.
- Rev. 5/11 10. Repeat any test not done within the prior 28 days.
- Rev. 5/11 11. Lipid profile should be fasting.

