7.2 Biological Sample Submissions

1. Pathological materials should be submitted for banking as outlined in Section [10](#) per patient consent.
2. Whole blood and plasma must be submitted as outlined in Section [11](#) for CYP2D6 status and tamoxifen and metabolite levels.

NOTE: It is required that biological sample submissions be logged into the ECOG-ACRIN Sample Tracking System (STS) (see Section [10.4](#)) for purposes of monitoring compliance.

NOTE: An informed consent must be signed prior to the use of any samples for any laboratory study or banking.

Rev. 8/12

	Pre-Study ¹	End of Cycle Three (3)	Off-Treatment	Submit to:
Block from Primary Tumor	X			ECOG-ACRIN Central Biorepository and Pathology Facility
Block from Metastatic Site (when available)	X			
Plasma (one (1) 6mL sodium heparin green top tube)*		X	X	
Whole Blood (one (1) 8-10mL EDTA purple top tube - K3)*	X ²			Indiana University School of Medicine

*Mandatory

1. Baseline, prior to treatment.
2. Whole blood is strongly encouraged to be collected at baseline, prior to treatment, but may be collected at the end of cycle three (3) if unable to collect at baseline.

8. Drug Formulation and Procurement

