8.1.12 References

- Legha SS. Tamoxifen in the treatment of breast cancer. Ann Intern Med 1988; 109:219-228.
- Love RR. Tamoxifen therapy in primary breast cancer: Biology, efficacy and side effects. J Clin Oncol 1989; 7:803-815.
- Please see tamoxifen package insert for more information.

9. Statistical Considerations

The primary purpose of this study is to evaluate whether patients with blood samples with CYP2D6 score of 0 (poor metabolizer) have a reduced progression-free survival (PFS) relative to patients with samples with a CYP2D6 score of 1 or 2 (intermediate and extensive metabolizers, respectively). A total of 240 patients will be enrolled in this study. Assuming a monthly accrual of 10 patients, 24 months of accrual is needed. The below calculations assume that 85% (204/240) of the patients enrolled have samples where a CYP2D6 score of 0, 1, or 2 can be assigned.

CYP2D6 SCORING

We will use a scoring system that has been recently modified from Gaedigk et al (18) to include known CYP2D6 variants and inhibitors:

CYP2D6 Allele	Points Assigned/Alele
*1, *1xN, *2, *2xN, *35	1
*9, *10, *17, *41	0.5
*3, *4, *5, *6, *11	0
Medication	Points Adjustment
Paroxetine, Fluoxetine, Bupropion	-2
Sertraline, Duloxetine, Citalopram, Escitalopram, Celecoxib, Diphenhydramine, Chlorpheniramine	-1
Venlafaxine	-0

An overall comparison of patients with scores CYP2D6=0 vs. CYP2D6= 1 or 2 with respect to progression-free survival will be made. It is estimated that approximately 10% will have a score=0, 40% with a score=1 and 50% with a score=2. A hazard ratio (HR) greater than 1.95 or 2 is of interest to influence change in practice. The table below shows the HRs that can be detected with 80% power when all patients have been followed at least 3 months and disease in 180/204 (88%) has progressed. A log-rank test with a 2-sided 5% type I error rate will be used for the comparison.

Hazard Ratios that can be detected with 80% power

Prevalence of patients with CYP2D6 Score=0				
8%		10%		12%
2.09		1.95		1.86

For example, if 10% of the patients have samples with a CYP2D6 score=0, there is 80% power to detect a hazard ratio of 1.95 (comparing score=0 to score=1 or 2).

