11.2 Sample Submission Schedule – Tamoxifen Metabolites (Mandatory)

Plasma must be collected at the following time points:

- End of Cycle 3
- Off Treatment

Questions pertaining to sample collection and shipment can be directed to [name] at the CBPF at [name] or [contact]. (International sites should contact [name] for special processing and shipping instructions.)

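### A CYP2D6 tube missed at baseline has one later scheduled draw, at the end of cycle 3, so a patient who stops before it has no scheduled genotype draw; the expected effect is small

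*Combined protocol and SAP*

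**What the plan says.** Four places give the same rule for the whole-blood tube.

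- Schema, note 2: the baseline collection "should be done prior to protocol treatment (preferred), but may be done at the end of Cycle 3 visit".
- Section 7.1, footnote 4: it is strongly encouraged that this blood "is collected prior to protocol treatment, but may be collected at the end of cycle three (3) if unable to collect at baseline".
- Section 7.2, footnote 2: it "may be collected at the end of cycle three (3) if unable to collect at baseline".
- Section 11.1.1: baseline, "but may be collected at the end of cycle three (3) if unable to collect at baseline".

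The Section 7.1 calendar also marks research blood at discontinuation of treatment, and the Schema note mentions blood at the end of treatment. Both send the reader to Sections 7.2 and 11 for what is submitted. Section 7.2 lists only the sodium heparin plasma tube in its off-treatment column. Section 11.2, on metabolites, says "Plasma must be collected at the following time points" and names the end of cycle 3 and off treatment. Section 11.2.1 turns that tube into plasma aliquots, whereas Section 11.3 takes DNA from whole blood.

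On imaging, Section 7.1 footnote 7 says that the scans needed to follow known disease "should be repeated at the end of Cycle 3 and then every 3 cycles during treatment". Section 9 assumes that "85% (204/240) of the patients enrolled have samples where a CYP2D6 score of 0, 1, or 2 can be assigned".

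**The concern.** The CYP2D6 score is the exposure in the primary objective. A patient without a score cannot enter the primary comparison or any estimate given by score.

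For a patient whose baseline tube was missed, getting a score depends on still attending at the end of cycle 3. The plan foresees earlier exits: Section 6.1.1 mentions objective progression before the end of cycle 1, and Sections 5.3 and 5.5 take patients off treatment for toxicity, withdrawn consent or a hold longer than 7 days. Where the exit is progression, the missing score is tied to the outcome. Under the trial's own hypothesis, score-0 patients progress early more often, so they would be lost slightly more often.

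At stake are a small upward shift in the by-score PFS and 6-month estimates, and a small fall in the observed share with score 0. Section 9 also uses that share in its feasibility rule.

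**Working it through.** **1. Is there another scheduled genotype draw?** No. The discontinuation mark in the Section 7.1 calendar leads by footnote 5 to Sections 7.2 and 11, which list plasma only at that time. Footnote 10, "Repeat any test not done within the prior 28 days", does not clearly reach a genotype tube that was never drawn. Tumor blocks are for banking, subject to consent.

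**2. Inputs.** From Section 9: 240 enrolled, 204 scored, 180 of 204 progressed, 24 months of accrual, at least 3 months of follow-up, 10% score 0, hazard ratio (HR) 1.95. Assumed, because the documents do not give them:

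- share d of baseline tubes missed: 5%, 15% or 30%;
- share c of events before day 84 that block the cycle 3 draw: 0.25 (lower case) or 1 (upper bound);
- exponential PFS.

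**3. The plan's own figure.** Take uniform accrual, the hazard that gives 180 of 204 events, and Var(log HR) = 1/d1 + 1/d0, where d1 and d0 are the events in score 0 and in scores 1+2. At 10% prevalence, d1 = 19.6 and d0 = 160.4. The HR detectable with 80% power is 1.95, as stated. The same method gives 2.09 at 8% and 1.86 at 12%, also as stated. The implied median PFS in scores 1+2 is 3.72 months.

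**4. Events before day 84 (2.76 months).** The monthly hazard in scores 1+2 is ln 2 / 3.72 = 0.186.

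- Scores 1+2: F1 = 1 − exp(−0.186 × 2.76) = 40.2%.
- Score 0: F0 = 1 − exp(−1.95 × 0.186 × 2.76) = 63.3%.
- Overall: 0.9 × 40.2% + 0.1 × 63.3% = 42.5%.

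**5. Loss and shift.**

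- Patients lost = 240 × d × c × 42.5%.
- Observed 6-month PFS in a group = S(6) / (1 − d × c × F).
- True values are 32.7% in scores 1+2 and 11.3% in score 0, a difference of 21.4 points.

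| c | d | lost of 240 | 6-month PFS, scores 1+2 | score 0 | difference (points) | observed score-0 share |
|---|---|---|---|---|---|---|
| 0.25 | 5% | 1 | 32.9% | 11.4% | 21.5 | 9.97% |
| 0.25 | 15% | 4 | 33.2% | 11.6% | 21.6 | 9.92% |
| 0.25 | 30% | 8 | 33.7% | 11.9% | 21.8 | 9.84% |
| 1 | 5% | 5 | 33.4% | 11.7% | 21.7 | 9.9% |
| 1 | 15% | 15 | 34.8% | 12.5% | 22.3 | 9.7% |
| 1 | 30% | 31 | 37.2% | 14.0% | 23.2 | 9.3% |

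Example, last row: 240 × 0.30 × 1 × 0.425 = 30.6 patients; 32.7% / (1 − 0.30 × 0.402) = 37.2%.

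**6. Longer PFS.** If the 180 events are reached 6 or 12 months after last entry, the median is 5.03 or 7.36 months. At d = 30% the loss is then 6 or 4 patients in the lower case, and 24 or 18 at the upper bound. For the 5.03-month median, 6-month PFS in scores 1+2 moves from 43.7% to 44.8% (lower) or 48.3% (upper). For 7.36 months it moves from 56.8% to 57.8% or 61.0%.

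**7. Hazard ratio, by simulation.** With 3,000 trials per cell at the 3.72-month median (Monte Carlo error about 0.01), the median estimated HR is:

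- 1.97 with no tubes missed;
- 1.98 and 1.99 at d = 15% and 30% in the lower case;
- 2.04 at d = 30% at the upper bound.

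The last shift is ln(2.035/1.973) / 0.232 = 0.13 standard errors of log HR. In a separate simulation with 204 patients, a 3.9-month median and true HR 1, rejection was 5.7% to 5.8% with 0%, 10% or 30% of tubes missed, so the missing tubes add no type I error.

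**The case against.** The cycle 3 provision is itself a rescue: without it, every patient with a missed baseline tube would be unscored. Baseline is the rule, the tube is mandatory, and samples are tracked. The first tumor assessment after baseline falls at the same visit as the later draw, so progression first found there does not prevent the tube. Section 9 already allows 240 − 204 = 36 unscored patients. Treatment can also stop for reasons that are not PFS events. Patients who stop without progressing stay in follow-up, and nothing forbids a late tube.

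All of this stands, and it is why the effect is small and the upper bound is not expected. It does not create a scheduled draw, however, and the allowance of 36 covers numbers, not selection by outcome.

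A reader might infer more, in three ways that the documents do not support.

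- *The primary comparison is biased.* The HR hardly moves, even at the upper bound.
- *The trial loses its stated power.* The largest loss in the table, 31, taken alone, is within 36. Power would fall only if the loss came on top of the 204: in simulation, from about 79% to 74% with 30% of tubes missed and every early event blocking the draw, and not noticeably if only a third did.
- *PFS results in general are too favorable.* Section 9 also summarizes response and 6-month status over all patients. Those summaries need no genotype, so only the by-score estimates are exposed.

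**Conclusion.** The point holds as a minor one. It is certain that the schedule leaves no genotype draw for a patient without a baseline tube who stops before the cycle 3 visit. The size of the effect is not known, because neither the share of missed tubes nor the share of early exits that block the draw is in the documents.

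Under the assumptions above, the lower case costs 1 to 8 patients of 240. At the 3.72-month median it raises by-score 6-month PFS by about 1 point or less and leaves the between-group difference within about 0.4 points. The observed score-0 share stays above 9.8%. The primary test is essentially unchanged. The case for acting is that the remedy costs almost nothing and score-0 patients are scarce.

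**What to change.** In Schema note 2, Section 7.1 footnote 4, Section 7.2 footnote 2 and Section 11.1.1, add one line: if no EDTA whole-blood tube has been collected by the time treatment stops, one is drawn at the off-treatment visit, whatever the reason for stopping.

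The cost is one extra tube, at a visit that already takes research blood, for the few patients without a baseline sample. Some loss through death or withdrawn consent will remain. If 20% of the blocked draws could not be recovered, 30% missed tubes would still leave 0.2 × 30.6 = about 6 patients unscored at the upper bound (6-month PFS in scores 1+2 of 33.5% against a true 32.7%) and 1 to 2 in the lower case.

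A table of missing genotype by time of and reason for stopping is optional. An added draw at the cycle 1 and 2 visits is not needed. Nor is a sensitivity analysis limited to baseline tubes, which could not detect an HR shift of 0.01 to 0.02 against a standard error of log HR of about 0.23.

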11.1.2 Sample Preparation Guidelines

Label blood samples with ECOG-ACRIN Protocol Number (E3108), ECOG-ACRIN Five Digit Sequence Number, Collection Date and Collection Time.

Whole Blood, EDTA purple top tube (Pharmacogenomics)

- Draw 8-10mL of blood into one (1) EDTA (purple top) vacutainer tube.
- Pipette whole blood into two (2) cryotubes of 4-5mL each.
- Freeze and store samples at -70°C or lower until time of shipment.

11.1.3 Shipping Procedures

Log the samples into the ECOG-ACRIN STS the day of shipment. If the STS is unavailable, an ECOG-ACRIN Generic Specimen Submission Form (#2981) must be submitted with the samples. Once STS is available, retroactively log the shipment into STS, using the actual collection and shipping dates.

Rev. 8/12

Frozen blood samples should be shipped the day after collection. Ship blood samples overnight on dry ice. Blood samples collected on Thursday or Friday should be shipped the following Monday.

Ship to:

[name]
Indiana University School of Medicine
Division of Clinical Pharmacology
[name]
[name]
[name]
[contact]
[contact]
[contact]

Email: [contact]

An STS shipping manifest form must be generated and shipped with all sample submissions.

Samples should not be shipped on Friday or the day before an observed holiday.

11.2 Sample Submission Schedule – Tamoxifen Metabolites (Mandatory)

Plasma must be collected at the following time points:

- End of Cycle 3
- Off Treatment

Questions pertaining to sample collection and shipment can be directed to [name] at the CBPF at [name] or [contact]. (International sites should contact [name] for special processing and shipping instructions.)

11.2.1 Sample Preparation Guidelines

Blood tubes should be labeled with the ECOG-ACRIN protocol number "E3108", patient initials, ECOG-ACRIN patient sequence number, institution name, date and time drawn and time point.

Rev. 8/12

Plasma, Sodium Heparin green top tube

- Draw 6mL of blood into one (1) sodium heparin (green top) vacutainer tube. Cover blood immediately after collection.
- Centrifuge tube at 4°C for 15 minutes at 3500 RPM.
NOTE: Tamoxifen metabolites are extremely sensitive. Work in low-light areas during processing (tin foil may be removed briefly while in centrifuge).
- Pipette plasma into three (3) cryotubes of 1mL each; place any remaining plasma into a fourth cryotube.
NOTE: Wrap each cryotube entirely with foil; a sample label must be placed on the cryotube itself and an additional label placed on the foil.
- Freeze and store samples at -70°C or lower until time of shipment.

